## **Background and Purpose**

### **Overview**

Veterans with serious mental illnesses (SMI) are at elevated risk for co-occurring medical conditions resulting in increased risk of disability, high health care spending, reduced quality of life and early mortality. Physical wellness is increasingly recognized as a key component of the VA's commitment to developing recovery-oriented treatment, promoting attention to interventions that promote and improve patient self-management of chronic medical conditions. The Chronic Disease Self-Management Program (CDSMP), a peer-facilitated group intervention that emphasizes training in disease self-management strategies, action planning, feedback and problem-solving, has been shown across multiple studies to improve health related attitudes and behaviors, health status and efficient utilization of medical services among adults with a range of chronic medical conditions. A recent adaptation of this program for SMI consumers found improved patient activation and health related quality of life, with effect sizes similar to those seen in CDSMP general population studies. In a separate contemporaneous effort, our team developed and evaluated a modified and enhanced version of the CDSMP called Living Well. Our results included significant improvement in somatic and mental health related attitudinal (self-efficacy, patient activation), behavioral (self-management behaviors) and functional outcomes (general health functioning, physical and emotional well-being) as well reduced emergency room use for medical care.

The VA has been a national leader in creating service delivery models integrating psychiatric and somatic care. To complement and enhance these systems-level initiatives, there remains an urgent need to establish and disseminate effective Veteran-centered self-management interventions, such as Living Well, that show promise for improving functional outcomes and limiting use of expensive emergency room visits for the management of chronic medical conditions. Also, although the VA is becoming a national leader in engaging and training peer specialists to help support mental health recovery and self-management, such efforts have not been extended to medical self-management services for SMI Veterans, thereby limiting the VA's capacity to adequately address the full recovery needs of Veterans. Further, little is known about how to best enhance the uptake, implementation and sustainability of peer programming related to medical illness self-management.

Building on the established efficacy of consumer facilitated medical illness self-management programming used in the general population and two recent adaptations for use with SMI adults in the public health sector (including our own evaluation of an intervention called Living Well), we propose to complete a randomized controlled effectiveness trial of our Living Well intervention and simultaneously conduct a well specified process evaluation to optimize knowledge accrual regarding important factors that may improve future adoption, implementation and sustainability of the Living Well intervention in the VA system of care.

### **Hypotheses**

The purpose of this study is to: 1. Complete an effectiveness trial of Living Well in the VA context, and; 2. Concurrently collect, in the context of a process evaluation, important contextual and cost information that can help speed throughout to public health impact.

For the remainder of this protocol all required descriptions will be presented first for the EFFECTIVENESS TRIAL and second for the PROCESS EVALUATION.

Objectives and hypotheses for the EFFECTIVENESS TRIAL:

Objective: Complete a randomized controlled effectiveness trial comparing Living Well to a general medical illness education and support group among SMI Veterans with co-occurring chronic medical conditions. Those receiving Living Well will demonstrate:

Hypotheses for EFFECTIVENESS TRIAL:

Primary Hypotheses (regarding functional and service-related outcomes)

Hypothesis 1: Improved general, physical, and emotional functioning post intervention.

Hypothesis 2: Lower rates of medical emergency room use for management of a chronic medical condition six months post randomization.

Secondary Hypotheses (regarding more proximal attitudinal and behavioral outcomes)

Hypothesis 3: Improved health-related self-efficacy and patient activation post intervention. Further, such improvements will mediate the effects of the functional and service outcomes specified above.

Hypothesis 4: Improved self-management behaviors post intervention. Further, such improvements will mediate the effects of the functional and service outcomes specified above.

Secondary Hypothesis (regarding retention of intervention effects)

Hypothesis 5: Sustained improvements across functional, attitudinal and behavioral outcomes for three months after completing treatment.

Objective for the PROCESS EVALUATION:

Complete a well specified process evaluation based on the RE-AIM evaluation framework to better understand contextual factors that can improve future adoption, implementation and sustainability of the Living Well intervention in the VA system of care. A cost analysis will also be completed as part of this effort.

## **Methodology**

### **Research Design**

Research Design for EFFECTIVENESS TRIAL:

The research design for the EFFECTIVENESS TRIAL will include a randomized trial (N=250) comparing participants assigned to the Living Well self-management intervention or the medical illness education and support comparison group. Using an intent-to-treat framework, we will collect data from every participant at four time points, at consent, at randomization, post-treatment (3 months from randomization assessment), and again 3 months later (6 months from randomization). Services data regarding use of the ER and other medical services including outpatient appointments with primary and

specialty care medical providers within the VA will be collected at the follow-up assessment (6 months from randomization) as this allows for a more realistic timeframe for assessing effects on service utilization. To inform related analyses we will also collect retrospective service utilization data for a full six months before consent. We will recruit participants from outpatient programs with the VAMHCS (Baltimore and Perry Point) and from the DCVA.

#### Research Design for PROCESS EVALUATION:

A well-specified process evaluation based on the RE-AIM Framework will be used to guide the PROCESS EVALUATION. The acronym stands for Reach, Effectiveness, Adoption, Implementation, and Maintenance which together determine public health impact. This evaluation will integrate findings from two streams of inquiry: 1) A qualitative study that combines focus groups and in-depth individual interviews conducted both before and after the clinical trial, and; 2) a cost analysis focused on implementation/operating costs and cost consequences.

#### Setting

Effectiveness Trial participants will be recruited from outpatient programs within the Baltimore and Perry Point VA Maryland Health Care System (VAMHCS) as well as the Washington, DC VA Medical Center.

#### Recruitment

Potential VA participants will be identified by several methods: (1) CPRS chart review and screening via use of partial HIPAA waiver, (2) VA clinician referrals of participants who meet inclusion criteria and who might be interested in participating, (3) Self referrals by participants who hear about the study and are interested in participating or who have participated in other MIRECC studies and have indicated a willingness to be contacted for studies in the future, (4) Self-referral via IRB approved study flyer (5) Use of the VAMHCS MIRECC Recruitment Database (Protocol # 00042721) to identify participants who meet study eligibility criteria.

Participants will be screened for eligibility via chart review. Study staff will then contact a VA treatment team member to determine if a potentially eligible participant is clinically stable enough to participate in the study and can be contacted for recruitment.

Per VA requirements, initial contact with veterans will be made in person or by letter prior to any telephone contact. Specifically, we will approach individuals before or after their VA appointments.

We will also send out a letter to the participant to see if they are interested in participating in the study. They will be given contact information for the study staff as well as a pre-stamped envelope and postcard to mail back to indicate their interest or lack of interest. A follow-up phone call will be made to ensure the participant received the mailing.

Further, it should be re-iterated that research assistants who will interact with participants are all specially trained to work with persons with serious mental illnesses. Research staff will first consult the participant's treatment team for permission to begin the consent process. This will help avoid approaching people who may be in crisis or may not be able to comprehend the study

procedures, risks, and benefits.

## **Participants**

1) *Effectiveness Trial Participants (Veterans):*

**Inclusion Criteria:** (1) Diagnosis of Schizophrenia/Schizoaffective disorder, bipolar disorder, major depression with psychotic features, psychosis NOS, or PTSD, (2) Age 18-80, (3) chart documented presence of at least one of the following chronic medical conditions: a respiratory condition, diabetes, arthritis, cardiovascular condition, (4) Receiving mental health services at a designated study site, (5) willing and able to provide consent to participate, (6) deemed clinically stable enough to participate in the study by a treatment provider.

**Exclusion Criteria:** (1) Serious cognitive impairments due to brain damage or injury, (2) Enrollment in ongoing studies at the MIRECC, A Randomized Control Trial of Ending Self-Stigma for PTSD and Improving Negative Symptoms and Community Engagement in Veterans with Schizophrenia.

2) *Clinicians and Stakeholders in the Process Evaluation Trial:*

**Inclusion Criteria:** (1) Employed by the VA as a national stakeholder, clinician or administrator as defined by: Stakeholder: National VA Central Office Staff affiliated with the Health Promotion and Disease Prevention Program, Office of Peer Services within the Psychosocial Rehabilitation and Recovery Services (PSR&R) section of the VA National Office of Mental Health Services, the VA's Office of Patient Centered Care, and the Primary Care-Mental Health Integration Program (PC-MHI). Clinician: local mental health providers and administrators associated with VA mental health treatment programs. (2) Willing and able to provide consent to participate in the Process Evaluation focus groups and/or individual interviews.

**Exclusion Criteria:** (1) None.

3) *Peer Facilitators in the Process Evaluation Trial:*

**Inclusion Criteria:** (1) Served as a peer facilitator for the Living Well group condition, (2) Willing and able to provide consent to participate in the Process Evaluation interview.

**Exclusion Criteria:** (1) None.

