### **Sample Size**

For EFFECTIVENESS TRIAL:

This Randomized Controlled Effectiveness Trial is powered to detect differences on the two primary outcomes: (1) significantly reduced proportion of participants with an ER visit at the 3-month follow-up assessment (6 months post randomization) in the Living Well condition versus control, (2) significantly improved health functioning at post-treatment in the Living Well condition versus control as measured by the SF-12.

ER Visits. In our prior pilot the proportion with an ER visit in the Living Well condition at the 3-month follow-up was 10.7% and in the control condition it was 27.6%. For this power calculation we assumed that the proportion with an ER visit in the Living Well condition at the 3-month follow-up will be 10.7%. However, since we have an active control in this proposal, we specify a lower percentage in the control condition (versus estimate from the pilot study) equal to 25%, and thus a 14.3 percentage point difference. With a two-tailed, alpha .05 level test, and power = .80 to detect this 14.3 percentage point difference we calculate that we will need n = 250 (125 per condition). The percentage point difference that can be detected could be somewhat higher or lower depending on the inter-correlations among the covariates and ER response variable. As proportion with an ER visit will be obtained from VA electronic medical charts for all randomized participants, loss to follow-up is not a significant concern for this outcome. This calculation is conservative -- we would actually have power equal to .80 to detect a smaller difference because the above calculation is based on a basic z-test of proportions, whereas the analysis model

specified above is more powerful. Calculation was performed using PASS version 11.0 (from NCSS, LLC) software. We acknowledge that use of the ER may be different in the VA context given the co-location of medical and psychiatric care, but as evidenced in our previous work (see section A.3), we found that veterans with SMI used the VA ER for medical care at rates comparable to (even greater than) those in our community sample. Specifically, the rate of use in the VA sample was 43% and the baseline rate in the Living Well sample was 31.3%.

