#### Data Analysis

##### FOR EFFECTIVENESS TRIAL:

Primary Hypotheses (regarding functional and service-related outcomes):

Hypothesis 1 (H1): Compared to those receiving a general medical illness education and support group, participants receiving Living Well will demonstrate greater improved general health functioning including both physical and emotional functioning.

To test the null hypothesis of no difference in improved general health functioning, we will use a longitudinal mixed effects model to compare change in mean physical and emotional health functioning from randomization to post-treatment. Regression equation (random effects not presented) at each time point will be:

SF12 function = Intercept + site + covariates + study condition + time + study-condition\*time + error

Notes: (1) Test of the null hypothesis of no difference in change from randomization to the post-treatment assessment will be conducted using a specified contrast. (2) "Study condition" is a dichotomous variable indicating study condition; (3) A random intercept and random slope (coefficient for time) will also be specified for the model; (4) The "time" variable will be entered as a continuous variable with possible values 0, 3, and 6 corresponding to the three assessment points (randomization, post-treatment, & 3-month follow-up); (5) The "covariates" terms represent adjustment for age, race, gender, and important potential confounders and will include Charlson comorbidity index score, chronic somatic illness

category, and any other covariate found to significantly differ at randomization (provided no significant collinearities are found). We are expecting few chance differences at randomization due to large sample size and random study condition assignment; (6) We have included a “site” term to adjust for site differences.

Hypothesis 2 (H2): Compared to the medical illness education and support group, the Living Well group will have a lower proportion of participants who will have had an emergency room visit for management of a chronic medical condition during the six months after randomization.

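### Psychiatric diagnosis defines eligibility but enters the H1 and H2 models only through a baseline significance test; prespecify it, with a time interaction in H1

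*Protocol*

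**What the plan says.** Participants, Effectiveness Trial inclusion criterion (1), lists schizophrenia or schizoaffective disorder, bipolar disorder and then "major depression with psychotic features, psychosis NOS, or PTSD". Any one of these suffices. Criterion (3) separately requires a chronic medical condition.

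The objective under Hypotheses is a comparison "among SMI Veterans with co-occurring chronic medical conditions". The protocol nowhere defines SMI by diagnosis.

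Data Analysis, Hypothesis 1, note (5) fixes age, race, gender, Charlson score and chronic somatic illness category as covariates, then adds "any other covariate found to significantly differ at randomization", subject to a collinearity check. Hypothesis 2, note (4) uses the same list and the same rule. Both models also carry a site term. Psychiatric diagnosis is named in neither.

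The exploratory analyses define five subgroups by medical condition, with subgroup effects and a global interaction test. Nothing equivalent is set out for psychiatric diagnosis. A generic moderator analysis covers demographic and clinical characteristics and points back to the list of measures, which contains no psychiatric diagnosis instrument.

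**The concern.** Eligibility has a psychiatric half and a somatic half, but only the somatic half has a fixed place in the primary models. Diagnosis must be established for every participant to confirm eligibility, and it plausibly predicts emotional functioning and ER use. Under the stated rule it is used only if the arms happen to differ significantly on it.

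In a randomized trial such a test measures chance. It says nothing about whether the factor predicts the outcome, which is the reason to adjust. The rule also means that the covariate set of both primary models cannot be written down before the baseline data are seen. What is at stake is some precision, a settled primary model, and clarity about the population to which the conclusion applies.

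**Working it through.** **1. The plan's own figures.** For ER visits, Sample Size sets the control rate "equal to 25%, and thus a 14.3 percentage point difference", with 10.7% in Living Well, two-sided alpha .05 and power .80. The pooled two-proportion formula gives 112 per arm, and with continuity correction 125 per arm, which is the stated number. For SF-12 (110 per arm, 0.40 SD, correlation .50), the stated power is .89. Standard formulas give .843 for change from one baseline and .929 for ANCOVA with one baseline and one post measure. The stated value lies between them, and the gap does not bear on this point.

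**2. When the rule would bring diagnosis in.** The protocol gives no PTSD share, so s is assumed. At 125 per arm the between-arm difference in share has SE = sqrt(2s(1−s)/125), and significance needs 1.96 × SE:

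| s | SE | Difference needed |
|---|---|---|
| 20% | 5.1 points | 9.9 points |
| 35% | 6.0 points | 11.8 points |
| 50% | 6.3 points | 12.4 points |

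If diagnosis groups differ by an assumed 0.4 SD in SF-12 change, an unadjusted 12-point imbalance moves the realised estimate by 0.12 × 0.4 = 0.048 SD, against a planned 0.40.

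**3. Bias and type I error.** That shift is the outer end of ordinary chance variation, which the standard error already covers. In a simulated ANCOVA (110 per arm, 35% PTSD, diagnosis effect 0.4 or 0.8 SD), type I error was .049 and .051 with diagnosis omitted, .047 and .052 with it always included, and .048 and .047 with it included only if significant.

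**4. Precision in H1.** With correlation .50 the variance of change is 2(1 − .50) = 1 SD². Omitting a factor that shifts change by δ adds δ²s(1−s). Power is Φ(0.40/sqrt(2V/110) − 1.96). At s = 35%:

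- adjusted, V = 1: .843
- omitted, δ = 0.4, V = 1 + 0.16 × 0.2275 = 1.036: .830, a loss of 1.3 points
- omitted, δ = 0.8, V = 1 + 0.64 × 0.2275 = 1.146: .791, a loss of about 5 points

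Simulations agree: the gain for H1 was about 0.5 to 5 points over the same range of δ. For H2 it was about 1 point, within simulation error.

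**5. Which term is needed in H1.** The H1 test is a condition-by-time contrast. With complete data at two time points it is a difference in mean change, and a term that is constant over time cancels from each person's change. Under a 12-point imbalance and a 0.4 SD effect on change, the simulated shift was 0.048 SD with diagnosis omitted and 0.048 SD with a diagnosis main effect added. With three time points and a random slope the two were again identical. Only a diagnosis-by-time term removes the shift.

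**6. Whether PTSD eligibility undermines the sample size.** The documents give no PTSD share, ER rate or effect. Over assumed shares of 20% to 50%, using the uncorrected formula at 125 per arm (reference power .844):

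- same relative effect, PTSD control rate 25%: unchanged at .844
- same relative effect, rate 15%: .805 to .737. At a 50% share, for example, control is .5 × .25 + .5 × .15 = .200 and Living Well is .200 × .107/.25 = .086.
- same relative effect, rate 43%: .899 to .952
- no effect in PTSD, rate 25%: .632 to .279

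The direction depends entirely on the assumption.

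**The case against.** The strongest reply is that little is lost. Randomization protects the test, type I error is unaffected, and the power cost is about 1 point unless diagnosis is strongly prognostic for change. That stands, and it limits the point to one of precision and prespecification.

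A second reply is that covariate and subgroup lists are commonly left to an analysis plan, that note (5) speaks of important potential confounders, and that the moderator analysis could include diagnosis. In part this is fair. But the protocol does not leave the matter open: it names the covariates and states the selection rule for any others, and that rule is the weak element.

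A reader might also infer that the criteria mix two populations, so that the objective contradicts eligibility and the planning figures are wrong for the enrolled sample. The documents do not support this. SMI is never defined, so the inclusion list can be read as its working definition. The earlier work is described as "two recent adaptations for use with SMI adults in the public health sector", but its diagnosis mix is not given, so it is not shown to have lacked PTSD. The remark that "we found that veterans with SMI used the VA ER for medical care at rates comparable to" those in the community sample, with its 43% rate, supports plausibility only; the calculation uses 10.7% and 25%.

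Nor is the absence of a severity threshold peculiar to PTSD, since none is set for any listed diagnosis.

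**Conclusion.** The point holds as a modest, specific improvement. Both primary models fix the somatic but not the psychiatric half of eligibility, and leave diagnosis to a baseline significance test that reflects chance rather than prognostic value. The consequence is some lost precision and a model that depends on the data: about 0.5 to 5 points of H1 power if diagnosis shifts SF-12 change by 0.4 to 0.8 SD at a 35% PTSD share (both assumed), and about 1 point for H2, not distinguishable from simulation error.

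The tests are not biased and type I error is not inflated. No stated power or sample size is shown to be wrong because PTSD is eligible. Whether PTSD counts as SMI needs clarifying, but it is not a demonstrated contradiction.

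**What to change.** - **H1 (Data Analysis, note 5):** make psychiatric diagnosis group (PTSD without a listed psychotic or bipolar diagnosis versus all others) a prespecified covariate with its interaction with time, in place of the baseline-significance rule for this factor. The interaction is essential, because a main effect alone does not alter the contrast tested.
- **H2 (note 4):** include the same factor as a prespecified main effect, optionally also by time.
- **Reporting:** give the H1 and H2 estimates by diagnosis group in a supportive table.
- **Population wording:** state whether PTSD is part of the trial's SMI population, so that the objective and the conclusion match the inclusion list.

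The cost is one or two degrees of freedom per model, one table and a few lines of text. No new data collection is needed, since diagnosis is established when eligibility is confirmed.
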